#### Sample size

The FDA has suggested that scientifically meaningful 'binning' of patients based on clinical characteristics can help guide future approval of specific patient groups for drug treatment. The present study is not intended for FDA submission or label expansion of Trikafta™, but as a means to determine whether iPS cells differentiated to respiratory phenotype can be used to predict clinical response to CFTR modulators. For the purposes of this protocol, the subjects enrolled, although potentially of different genotypes, will represent a scientifically meaningful cohort or 'bin' of individuals with partial function mutations, sweat chloride < 80 mmol/L, and/or pancreatic sufficiency. This protocol is designed to compare *in vitro* responsiveness of differentiated iPS cells to *in vivo* clinical activity of Trikafta™, and will test the null hypothesis that the true Trikafta™ response rate of CFTR individuals with partial function mutation genotypes is  $\leq 10\%$  vs. the alternative hypothesis that the true Trikafta™ response rate is  $\geq 40\%$ . We will initially enroll four subjects, and expect all of these individuals will show a clinical response (e.g.,  $> 5\%$  improvement of % predicted FEV1 from baseline). If none of the first four subjects exhibit a response, the study will be terminated. Otherwise, we intend to enroll a total sample size of 22 individuals. Subjects who do not complete the study will be replaced. In this design, if Trikafta™ is ineffective, the probability of early termination after four subjects is 66% and only a 5% chance of concluding the drug is effective (type I error). If Trikafta™ is effective, there is an 86.4% chance of reaching this conclusion. If fewer than four patients show a clinical effect, Trikafta™ will be considered ineffective. To demonstrate the ability of iPS cells to predict clinical benefit, 22 patients will provide at least 80% power to detect a significant correlation of at least  $r = 0.55$  between the changes in clinical outcomes with changes in short circuit current as measured in iPS cells. Tabular details of this analysis are provided below. Power calculations were performed using PASS v. 14 (Kaysville, UT) with a two-sided Z-test and a significance level of 0.05.

	Cumulative # of responses	Decision	95% Confidence Interval (CI)

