Stage 1: Enter 4 subjects	0	Terminate the trial because the agent is ineffective. Response rate is <math>\leq 10\%</math>	LB of 95% CI is $< 10\%$
	At least 1	Inconclusive result, continue trial (proceed to stage 2).	95% CI contains 10% and the UB is $< 40\%$

Stage 2: Enter 18 additional subjects	4 or less (stage I + stage II)	Consider that the agent is ineffective. Response rate is $\leq 10\%$	LB of 95% CI is less than 10%
	5 or more (stage I + stage II)	Drug may be effective Response rate is greater than 10% and not different from 40%	95% CI contains 40% and LB is $> 10\%$
	14 or more (stage I + stage II)	Drug is effective Response rate is at least 40%	95% CI LB $\geq 40\%$

LB = Lower Bound, UB = Upper Bound

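### The Substudy 1 decision table reads 0 of 4, or 4 or fewer of 22, as showing a response rate of at most 10%, which those counts cannot show

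*Combined protocol and SAP*

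**What the plan says.** Section 11 (Statistical Methods), under Sample size for Substudy 1, tests a null response rate of at most 10% against an alternative of at least 40%, in two stages: "Stage 1: Enter 4 subjects", then "Stage 2: Enter 18 additional subjects", 22 in total. On the first stage the text says: "If none of the first four subjects exhibit a response, the study will be terminated".

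The decision table then gives conclusions:

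- 0 of 4 responders: "Terminate the trial because the agent is ineffective", with the response rate stated to be at most 10%.
- 4 or fewer of 22: "Consider that the agent is ineffective", with the same statement about the rate.

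In both rows the confidence-interval column requires only that the lower 95% bound lie below 10%. No row that concludes ineffectiveness sets a condition on the upper bound.

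Two other places bear on the point. The Substudy 1 methods text promises an approximate binomial 95% interval with the overall response rate, without naming the method. The Sample size text declares the drug ineffective when fewer than four patients respond, whereas the table's cutoff is four or fewer.

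**The concern.** A lower bound below 10% means the data have not shown the rate to be above 10%. To conclude that the rate is at most 10%, the upper bound would have to be at or below 10%. The table uses the first condition to support the second conclusion, so a failure to reject the null is written as proof of the null.

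What is at stake is what the trial may pre-specify as its negative finding. With four subjects, or with 22 subjects of whom up to four respond, the plan would commit the investigators to a parameter statement that the reported interval contradicts. At 3 of 22 (13.6%) and 4 of 22 (18.2%), the observed rate itself is above 10%.

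**Working it through.** **Inputs (Section 11, Sample size and decision table).** Null 10%, alternative 40%; stage 1 n = 4, stop at 0 responders; total n = 22; ineffective at 4 or fewer; success at 5 or more.

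**1. The plan's own figures.** With p the true rate:

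- Early stop = (1 − p)^4. At 10%: 0.9^4 = 65.6% (plan: 66%).
- Success = Σ over x = 1..4 of P[Bin(4,p) = x] × P[Bin(18,p) ≥ 5 − x]. At 10%: 4.4% (plan: 5%). At 40%: 85.6% (plan: 86.4%).

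The early-stop and power figures reproduce closely, and 5% serves as a ceiling on the type I error. With success at 4 or more, the type I error would be 10.75%, so 5 or more appears to be the intended rule.

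**2. Interval after 0 of 4.**

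- Exact upper limit: 1 − 0.025^(1/4) = 60.2%.
- Wilson upper limit: z²/(n + z²) = 3.84/(4 + 3.84) = 49.0%.
- Agresti-Coull: 54.6%.
- Wald: 0 ± 1.96 × √(0 × 1/4), which collapses to 0–0 and carries no information.

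Every usable limit listed is far above 10% and also above 40%.

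**3. Interval after 4 of 22 (observed 18.2%).**

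- Wald: 0.182 ± 1.96 × √(0.182 × 0.818/22) = 2.1% to 34.3%.
- Wilson: 7.3% to 38.5%.
- Agresti-Coull: 6.7% to 39.1%.
- Exact: 5.2% to 40.3%. It includes 40% by a narrow margin: P(4 or fewer of 22) at a true 40% is 0.0266, just above 0.025.

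**4. Lower counts in the same row.** The exact upper limit is 34.9% at 3 of 22, 29.2% at 2 and 22.8% at 1. One is the smallest count that can reach stage 2. Even a hypothetical 0 of 22 gives 1 − 0.025^(1/22) = 15.4%. With no responders at all, an exact two-sided 95% upper limit of 10% or less needs 36 subjects (29 for a one-sided 95% limit). By the exact interval, then, no outcome in either row supports the statement.

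**5. How often the conclusion is reached.** P(ineffective) = (1 − p)^4 + Σ over x = 1..4 of P[Bin(4,p) = x] × P[Bin(18,p) ≤ 4 − x].

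At p = 0.20: 0.4096 + (0.4096 × 0.5010 + 0.1536 × 0.2713 + 0.0256 × 0.0991 + 0.0016 × 0.0180) = 0.4096 + 0.2495 = 0.659.

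| True rate | Stop at 0 of 4 | Total, table's cutoff (4 or fewer) | Total, text's cutoff (fewer than 4) |
|---|---|---|---|
| 20% | 41.0% | 65.9% | 53.6% |
| 25% | 31.6% | 47.6% | 38.2% |
| 30% | 24.0% | 32.5% | 26.9% |
| 40% | 13.0% | 14.4% | 13.3% |

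**The case against.** The best defence is that these are decision labels in an ordinary two-stage design. The column is a decision column, and the 10% figure merely repeats the null hypothesis. The operating characteristics broadly reproduce, and no decision, sample size or error rate depends on the wording. The methods text also requires a confidence interval, so a bare claim would not be reported alone. The plan discloses a power of 86.4%, hence a risk of about 14% of missing a true 40% rate. The larger probabilities above come from true rates between the two hypotheses, where the design promises nothing.

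Much of this stands. The stopping rule is sound, and the 14% at the target agrees with what the plan discloses. But a futility rule supports stopping, or saying that a rate above 10% was not shown. It does not support a statement about where the true rate lies, and reporting the interval would only put the contradiction on the page.

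A reader might infer two stronger things that the documents do not support. One is that the stage 2 row is generally compatible with the 40% target. That holds only at exactly 4 of 22 and only with the exact interval; the plan calls for an approximate one, and Wald, Wilson and Agresti-Coull all exclude 40%. The other is that the wording would cost patients access to the drug. Section 10 does foresee sharing results with insurers and the manufacturer, but it also says the data are not meant for regulatory submission or label expansion. Nothing ties this table to an access decision.

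**Conclusion.** The point holds as a fault of stated inference, not of design. After 0 of 4 the data exclude neither rates above 10% nor the 40% target (upper limit 49% to 60%, Wilson to exact). After 4 of 22 they do not exclude rates well above 10% (upper limit 34% to 40%, Wald to exact), while 40% is excluded by every interval computed here except the exact one. Under the table's cutoff, a drug with a true response rate of 20%, 25% or 30% would be recorded as having a rate of at most 10% in 66%, 48% or 32% of trials; at a true 40% the figure is 14%.

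These results assume independent subjects with a common response probability, no missing outcomes, and fixed-sample intervals that ignore the two-stage sampling. The probabilities depend on which cutoff is meant: with the text's fewer-than-four rule they fall to 54%, 38%, 27% and 13%. The conclusion about the wording does not depend on that choice.

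**What to change.** - Delete the statement that the response rate is at most 10% from both rows.
- After 0 of 4, write: *stop for futility; a response rate above 10% not shown (exact 95% CI 0–60%)*.
- After 4 or fewer of 22, write: *response rate not shown to exceed 10%*, with the interval.
- Name an exact or Wilson interval in place of the unspecified approximate one, since Wald is unusable at 0 of 4.
- Bring the Sample size sentence that declares the drug ineffective into line with this wording, and reconcile its cutoff of fewer than four with the table's four or fewer.

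The cost is an edit to two table rows and two sentences. The sample size and the stage 1 stopping rule do not change. The type I error and power stay as calculated if the table's cutoff is the one kept; if the text's cutoff is kept, they need restating (type I error 10.75%).

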#### 11. Statistical Methods For a proposed open-label prospective 4-week trial of Trikafta™.

**Substudy 1:** Patients with CF or CFTR-dependent illness who do not have access to modulator therapy but exhibit a clinical phenotype suggestive of partial/residual CFTR activity.

We will serially evaluate clinical outcomes of interest prior to and after the start of therapy. Change in clinical measurements (spirometry, weight/BMI, quality of life, sweat chloride) will be monitored. Our main goals are to determine the clinical response to Trikafta™ and to determine if *in vitro* responsiveness of iPS cells predicts clinical response. The primary outcome is response to Trikafta™ after 4 weeks of treatment. In this study a clinical response to Trikafta™ at week 4 of treatment will be defined as an improvement, from baseline, in  $FEV_1 > 5\%$  predicted and each subject will be classified a responder or non-responder. In this study, if at least 40% of subjects meet the definition of responder, the drug will be considered efficacious (i.e., comparable to the benefit which led to Orkambi™ approval by FDA following trials in F508del homozygotes). Overall response rate will be accompanied by an approximate binomial 95% confidence interval. To determine the role of iPS *in-vitro* response to Trikafta™, we will compare the  $\Delta Isc$  (change in  $Isc$ ) among Trikafta™ responders and Trikafta™ non-responders using a two-sample t-test or a Wilcoxon rank sum test if distributions are skewed. Additionally, we will correlate the  $\Delta Isc$  obtained from *in vitro* experiments with the change in  $FEV_1\%$  predicted (post minus pre) using Spearman's rank-order correlation with an associated 95% confidence interval. We will also test whether the iPS response reaches a CFTR functional threshold of 40% wild-type levels (a magnitude of activity in primary airway epithelial cells viewed as potentially relevant to clinical benefit). In a sensitivity analysis, we will replicate the  $FEV_1$  analysis with sweat chloride responses, and determine the *in vivo* response rate.

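### One Stage 1 confidence-limit entry in the Substudy 1 decision table is impossible, and the Stage 2 entry for five or more responders depends on an interval method that the plan does not name

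*Combined protocol and SAP*

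**What the plan says.** Section 11 (Statistical Methods, Substudy 1) makes the responder rate at week 4 the primary outcome and states: "Overall response rate will be accompanied by an approximate binomial 95% confidence interval". It does not say which approximate interval.

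The Sample size text sets a null response rate of at most 10% against an alternative of at least 40%, in two stages: "Stage 1: Enter 4 subjects", then "Stage 2: Enter 18 additional subjects". The stop is given as a count: "If none of the first four subjects exhibit a response, the study will be terminated". With one or more responders the trial goes on to 22 subjects in all.

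The decision table then lists responder counts, decisions and a 95% confidence interval column:

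- Stage 1, no responders: lower bound below 10%.
- Stage 1, one or more: "95% CI contains 10% and the UB is" below 40%.
- Stage 2, four or fewer in total: lower bound below 10%.
- Stage 2, five or more: "Response rate is greater than 10% and not different from 40"%, with the interval entry "95% CI contains 40% and LB is" above 10%.
- Stage 2, fourteen or more: lower bound at least 40%.

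**The concern.** With four subjects a 95% interval is very wide, so an upper bound below 40% after at least one response looks unattainable. The row is also wrong for the outcome the plan expects, since the Sample size text anticipates a response in all four of the first subjects, and 4 of 4 cannot give an interval containing 10%.

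In Stage 2 the count rule works at roughly a one-sided 5% error, while the lower limit of a two-sided 95% interval is a one-sided 2.5% criterion. The two need not share cut-offs. If they differ, the report could conclude that the response rate exceeds 10% beside an interval that contains 10%. With the method unnamed, the choice of interval could also be made after the count is known.

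**Working it through.** **Inputs** (Substudy 1 Sample size text and table): null 10%, alternative 40%; stop at 0 of 4; 18 more subjects, 22 in all; success at 5 or more.

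**The plan's own figures first.** With X1 ~ Bin(4, p) and X2 ~ Bin(18, p):

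P(success) = sum over x1 = 1 to 4 of P(X1 = x1) × P(X2 ≥ 5 − x1)

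- Early stop at p = 0.10: 0.9^4 = 0.656 (stated 66%).
- Type I error at p = 0.10: 0.0436 (stated 5%).
- Power at p = 0.40: 0.856 (stated 86.4%, within one percentage point).

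A cut-off of 4 would give a type I error of 0.1075, so the table's cut-off of 5 is the one that fits the stated error rate. (The Sample size text puts failure at fewer than four, which differs from the table at exactly four. That is a separate point; the table's rule is used here.)

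**Interval formulas**, with z = 1.96:

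- Wald: p̂ ± z √[p̂(1 − p̂)/n].
- Wilson: (x + z²/2)/(n + z²) ± [z/(n + z²)] √[n p̂(1 − p̂) + z²/4].
- Exact (Clopper-Pearson): the upper limit solves P(X ≤ x | p) = 0.025; the lower limit solves P(X ≥ x | p) = 0.025.

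**Stage 1.** At 1 of 4 the upper limits are:

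- Wald: 0.25 + 1.96 × √(0.25 × 0.75/4) = 0.25 + 0.424 = 67.4%.
- Wilson: 0.3725 + 0.3269 = 69.9%.
- Exact: 80.6%.

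| Responders of 4 | Wald | Wilson | Exact |
|---|---|---|---|
| 1 | 0–67.4% | 4.6–69.9% | 0.6–80.6% |
| 2 | 1.0–99.0% | 15.0–85.0% | 6.8–93.2% |
| 3 | 32.6–100% | 30.1–95.4% | 19.4–99.4% |
| 4 | 100–100% | 51.0–100% | 39.8–100% |

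The lowest upper limit in the table is 67.4%. Dropping to 90% confidence only lowers it to 60.6%. The interval excludes 10% at 3 and 4 of 4 under all three methods, and at 2 of 4 under Wilson.

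**Stage 2.** At 5 of 22 (p̂ = 0.2273) the lower limits are:

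- Wald: 0.2273 − 1.96 × 0.0893 = 5.2%.
- Wilson: 0.2678 − 0.1666 = 10.1%.
- Exact: 7.8%.

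| Responders of 22 | Wald lower | Exact lower | Wilson lower |
|---|---|---|---|
| 4 | 2.1% | 5.2% | 7.3% |
| 5 | 5.2% | 7.8% | 10.1% |
| 6 | 8.7% | 10.7% | 13.2% |
| 7 | 12.4% | 13.9% | 16.4% |
| 13 | 38.5% | 36.4% | 38.7% |
| 14 | 43.5% | 40.7% | 43.0% |

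The first count with a lower bound above 10% is 7 (Wald), 6 (exact) or 5 (Wilson). The lower-bound entries for 0, for four or fewer, and for fourteen or more hold under all three.

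**Chance of landing where count and interval disagree**, from the two-stage distribution:

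| True rate | Total 5 or 6 (Wald conflict) | Total 5 (exact conflict) | Wilson conflict |
|---|---|---|---|
| 10% | 4.0% | 3.0% | none |
| 20% | 22.9% | 12.8% | none |
| 40% | 9.6% | 3.1% | none |

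**If the interval were made the criterion instead of the count**, power at 40% would fall from 85.6% to 82.5% (6 or more, exact) or 76.0% (7 or more, Wald).

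**The case against.** The strongest defence is that the count, not the interval, is the rule. The table runs from number of responses to decision, the text states the stop and the failure rule only as counts, and section 11 has the interval merely accompany the response rate. This largely stands: enrolment, stopping and error rates follow from the counts, and the stated design figures reproduce closely. A reader might infer that the Stage 1 entry, taken as a condition, would prevent any result from reaching Stage 2. The documents do not support that, because continuation is set by the count.

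A reader might also infer that the planned interval contradicts the count rule at both 5 and 6 responders. That would require the plan to specify Wald, and it does not. Wilson is equally an approximate binomial interval and agrees with every Stage 2 lower-bound entry. Nor is the whole interval column wrong, as most entries are attainable.

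The Stage 1 entry may be a reversed inequality. The text cannot show this, and reversing it would still leave the claim about containing 10% false at 3 and 4 of 4. The defence does not remove the need to name the method, because that choice decides whether the primary result agrees with its own table.

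**Conclusion.** The point holds in two parts. The Stage 1 entry for one or more responders is impossible under any usual method: the upper bound is at least 67.4% where the table says below 40%. This part needs no assumption about the method.

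The Stage 2 entry for five or more is conditional: false at 5 and 6 if Wald is used, false at 5 only if exact, and true under Wilson. The disagreement probabilities assume independent responses with a common true rate and the table's cut-off of 5.

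Severity is minor to moderate. The operating characteristics of the count rule are unaffected; the risk is an incoherent report of the primary outcome. The figures do not support saying that the design's error control or power is invalid.

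**What to change.** 1. Delete the Stage 1 interval entry for one or more responders, or correct it: the upper bound exceeds 40% at every such count, and whether 10% is included depends on the count.
2. State that the responder count is the decision rule and that the interval is descriptive.
3. In section 11, replace the unnamed approximate interval with a named one that agrees with the Stage 2 cut-offs. Either of two would do:
   - **Wilson 95% interval.** Lower bounds are 7.3% at 4, 10.1% at 5, 38.7% at 13 and 43.0% at 14. It keeps the stated 95% level but ignores the Stage 1 stop, and clears 10% only narrowly at 5.
   - **Exact two-stage one-sided 95% lower bound**, solving P(continue and total ≥ x | p) = 0.05. It gives 7.6%, 10.4%, 39.6% and 44.0% at the same counts. It respects the stop and matches the one-sided 5% error, but must be labelled one-sided 95% (90% two-sided).

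The cost is wording in section 11 and the table, settled before the responder count is known. Sample size, visits and the count rule do not change. The second option gives up the two-sided 95% level and needs a short program.

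### Substudy 1's decision table labels 5 to 13 of 22 responders as no different from 40% only because the interval fails to exclude 40%; a drug with a true 20% rate gets that label in 34% of trials by the count column

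*Combined protocol and SAP*

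**What the plan says.** Section 11, Sample size, sets up a two-stage single-arm design for Substudy 1. The plan "will test the null hypothesis that the true Trikafta™ response rate of CFTR individuals with partial function mutation genotypes is" 10% or less, against "the alternative hypothesis that the true Trikafta™ response rate is" 40% or more. On enrolment it says "We will initially enroll four subjects", then "If none of the first four subjects exhibit a response, the study will be terminated". With at least one responder among them, 18 further subjects bring the number to 22.

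The decision table that follows has three Stage 2 outcomes:

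- **4 or fewer responders:** ineffective.
- **5 or more:** the drug may be effective, with the statement "Response rate is greater than 10% and not different from 40" per cent. The interval column gives the basis: "95% CI contains 40% and LB is" above 10%.
- **14 or more:** effective, with a rate of at least 40% and a lower bound at or above 40%.

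Because 14 or more has its own row, the middle row covers 5 to 13. No margin around 40% is given.

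The opening text of Section 11 for Substudy 1 has a different rule. It regards the drug as efficacious if at least 40% of subjects are responders, and glosses this as "comparable to the benefit which led to Orkambi™ approval by FDA following trials in F508del homozygotes". It also promises the overall response rate with an approximate binomial 95% interval, without naming the method.

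**The concern.** The middle row makes two statements of different kinds. That the rate exceeds 10% is the result of a test against the null. That it does not differ from 40% is only a null that was not rejected, in a sample of 22, with no margin to say how close is close enough. A wide interval containing 40% also contains many rates well below it.

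The row matters because it is where the trial will most probably end if the drug performs as hoped. At a true 40%, 83.5% of trials finish there and 2.1% reach 14 or more. The label also sits awkwardly beside the 40% criterion in the opening text. At 5 to 8 responders, one part of Section 11 withholds the efficacy conclusion while another says the rate does not differ from that same 40%. Section 10 says the results will be offered to the manufacturer, insurers, the CF Foundation and families, who could take the label at face value.

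**Working it through.** **Inputs.** All are from Section 11: null 10%, alternative 40%, 4 subjects in stage 1 with a stop at 0 responders, 18 more in stage 2, and table cutoffs of 5 and 14. The true rate of 20%, half the benchmark, is my own scenario and is not a figure in the plan; other rates are shown below.

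**Formula.** P(total in range) = sum over a = 1 to 4 and c = 0 to 18 of Bin(a; 4, p) × Bin(c; 18, p), keeping only pairs with a + c in the range.

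**The plan's own figures first.**

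- Early stop at 10%: 0.9^4 = 0.656 (plan: 66%).
- Type I error with cutoff 5: 0.044 (plan: 5%, matched only as a rounded or nominal ceiling).
- Power at 40% with cutoff 5: 0.856 (plan: 86.4%).
- A cutoff of 4 would give power 0.867 but type I error 0.108, so the stated figures belong to the table's cutoff of 5.

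**Does the 40% clause ever fail within the row?** 95% limits at n = 22:

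| Responders | Observed | Wald | Wilson | Exact |
|---|---|---|---|---|
| 5 | 22.7% | 5.2 to 40.2% | 10.1 to 43.4% | 7.8 to 45.4% |
| 13 | 59.1% | 38.5 to 79.6% | 38.7 to 76.7% | 36.4 to 79.3% |
| 14 | 63.6% | 43.5 to 83.7% | 43.0 to 80.3% | 40.7 to 82.8% |

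Wald check at 5/22: 0.2273 ± 1.96 × √(0.2273 × 0.7727 / 22) = 0.2273 ± 0.1751.

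The upper limit is already above 40% at 5 responders and stays above it at higher counts. The lower limit does not reach 40% until 14. So 40% lies inside the interval at every count from 5 to 13 by all three methods, and no count that clears the cutoff of 5 can be found to be below 40%.

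**How often a 20% drug gets the label (count column).**

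- P(5 or more of 22), ignoring the stop: 0.4571.
- Remove trials that stopped at 0 of 4 but would have reached 5 in the next 18. P(0 of 4) = 0.8^4 = 0.4096. P(5 or more of 18) = 1 − (0.0180 + 0.0811 + 0.1723 + 0.2297 + 0.2153) = 0.2836. Product: 0.1162.
- 0.4571 − 0.1162 = 0.341. P(14 or more) is about 0.00001, so the 5-to-13 figure is the same, 34.1%.

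At other true rates: 16.3% at 15%, 52.4% at 25% and 67.4% at 30%.

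**If the interval column governs instead.** The row also requires a lower bound above 10%. At 5/22 only Wilson meets this (10.1%).

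| Method | Row starts at | P(label) at true 20% |
|---|---|---|
| Wilson | 5 | 34.1% |
| Exact | 6 (lower limit 10.7%) | 21.3% |
| Wald | 7 (lower limit 12.4%) | 11.2% |

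**Against the 40% criterion in the opening text.** 8/22 = 36.4% and 9/22 = 40.9%, so that criterion means 9 or more. At a true 20%, the two-stage P(9 or more) = 1.8%. Hence 34.1 − 1.8 = 32.3 points, about 32 of the 34, come from 5 to 8 responders (observed 23% to 36%).

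**The case against.** The table is more careful than the one clause suggests. The row's decision is only that the drug may be effective. The basis is printed beside it, and the claim of at least 40% is reserved for 14 or more responders. That already separates 40% not excluded from 40% shown. The plan also requires the rate with its interval, so at 5/22 a reader would see a wide range. It says the data are not for FDA submission or label expansion. Finally, 20% lies between the null and the alternative, where intermediate pass rates are ordinary for such a design.

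Much of this stands. The cutoff is not at fault and the row's decision is moderate. What remains is the rate statement beneath that decision, which the data cannot support at any count in the row.

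Three stronger readings are tempting, and the documents do not bear them out:

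- **That a partly effective drug would be reported as matching the approved-modulator benchmark.** The comparability wording is attached to an observed share of at least 40%, not to the 5-to-13 row. A 20% drug meets that criterion in 1.8% of trials.
- **That results in this row cannot be told apart from a rate of 10% to 20%.** This fits the low counts only. At 9/22 the lower limits are 20.4% (Wald), 23.3% (Wilson) and 20.7% (exact), all above 20%.
- **That comparability should be allowed only at 14 or more responders.** This would change a criterion rather than its wording. At a true 40%, the chance of reaching that conclusion would fall from 51% (9 or more) to 2% (14 or more).

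**Conclusion.** The point holds as a fault in a stated conclusion, not in the design. The middle row presents non-exclusion of 40% as a finding about 40%, and the clause is automatic at every count from 5 to 13. At a true 20% the label is reached in 34% of trials by the count column, and in 11% to 34% across interval methods if the lower-bound condition is enforced. Nearly all of the 34% comes from 5 to 8 responders, where the table's label and the 40% criterion in the same section pull in different directions.

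These figures assume independent responses with a common rate, all 22 subjects evaluable, the stage 1 stop applied as written, and limits computed as for a single sample of 22. The 20% rate is illustrative; the automatic nature of the clause does not depend on it.

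**What to change.** In the Stage 2 row for 5 or more responders:

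1. Replace the second half of the rate statement so that it reads along these lines: *rate above 10%; 40% neither shown nor excluded*.
2. Report the observed rate with its 95% interval, as Section 11 already requires.
3. Add that 5 to 8 responders do not meet the section's criterion of at least 40% of subjects, so that the table and the opening text agree.

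Leave the counts, sample size, stopping rule and the 9-of-22 criterion unchanged, and do not move the comparability wording to 14 or more.

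The cost is an edit to one table row and one added sentence, with no new subjects, data or analyses. The downside is a weaker permitted claim at 5 to 13 responders.
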